# 30.4.3 Sensitivity to Enrollment Rate

In this section, we repeat the operating characteristics of the previous section under different trial enrollment rates. Table 6 and Table 7 show the probability of success for the 5 different categories under the fast and slow enrollment rates respectively.

In this simulation, there is little to no impact from different enrollment rates on overall power, and notably, all values are about 81.7% when the true PAE rate is 7% and the true failure-free rate is 65%. However, it seems there is some impact on the early success rate for different enrollment rates since the amount of information available at the time of the interim is changed according to the enrollment rate. If the enrollment is slower than expected, the trial has a little higher ability to reach a success decision before the final analysis. With the fast enrollment, the trial has a lower ability to reach early success.

Failure-free			Pr(Declaring S	uccess)		
Rate	PAE Rate	Both	Effectiveness	Safety	Early	Final
0.50	0.07	0.009	0.010	0.855	0.002	0.007
	0.08	0.007	0.010	0.706	0.001	0.006
	0.1	0.005	0.010	0.342	0.001	0.004
	0.12	0.001	0.010	0.100	0.000	0.001
	0.14	0.000	0.009	0.023	0.000	0.000
0.55	0.07	0.132	0.155	0.861	0.040	0.092
	0.08	0.107	0.151	0.705	0.030	0.077
	0.1	0.054	0.154	0.345	0.016	0.039
	0.12	0.015	0.144	0.102	0.005	0.009
	0.14	0.004	0.153	0.021	0.001	0.003
0.60	0.07	0.539	0.620	0.866	0.237	0.302
	0.08	0.453	0.631	0.712	0.208	0.245
	0.1	0.216	0.629	0.336	0.095	0.121
	0.12	0.063	0.616	0.100	0.026	0.037
	0.14	0.013	0.618	0.022	0.006	0.008
0.65	0.07	0.818	0.951	0.859	0.621	0.196
	0.08	0.669	0.957	0.700	0.503	0.166
	0.1	0.316	0.952	0.330	0.239	0.076
	0.12	0.097	0.953	0.101	0.073	0.024
	0.14	0.021	0.954	0.022	0.016	0.006
0.70	0.07	0.847	0.999	0.848	0.817	0.030

# Table 6: Pr(Declaring Success) (Fast Enrollment)

0.08	0.683	0.999	0.684	0.658	0.025
0.1	0.347	0.999	0.348	0.334	0.014
0.12	0.102	0.999	0.102	0.099	0.003
 0.14	0.021	0.999	0.021	0.021	0.000

# Table 7: Pr(Declaring Success) (Slow Enrollment)

Failure-free	Pr(Declaring Success)					
Rate	PAE Rate	Both	Effectiveness	Safety	Early	Final
0.50	0.07	0.007	0.009	0.862	0.002	0.006
	0.08	0.006	0.008	0.708	0.002	0.004
	0.1	0.004	0.010	0.334	0.002	0.002
	0.12	0.001	0.008	0.101	0.000	0.001
	0.14	0.000	0.008	0.022	0.000	0.000
0.55	0.07	0.136	0.155	0.868	0.051	0.085
	0.08	0.111	0.158	0.694	0.038	0.072
	0.1	0.053	0.155	0.335	0.015	0.038
	0.12	0.015	0.146	0.102	0.005	0.010
	0.14	0.003	0.146	0.023	0.001	0.003
0.60	0.07	0.546	0.632	0.857	0.299	0.247
	0.08	0.434	0.623	0.691	0.238	0.195
	0.1	0.206	0.612	0.337	0.113	0.093
	0.12	0.064	0.610	0.099	0.035	0.029
	0.14	0.012	0.609	0.020	0.007	0.006
0.65	0.07	0.816	0.955	0.855	0.670	0.146
	0.08	0.676	0.961	0.705	0.560	0.116
	0.1	0.327	0.954	0.342	0.262	0.065
	0.12	0.101	0.952	0.104	0.083	0.018
	0.14	0.019	0.948	0.020	0.015	0.004
0.70	0.07	0.850	1.000	0.850	0.834	0.016
	0.08	0.700	0.999	0.700	0.685	0.015
	0.1	0.324	0.999	0.324	0.318	0.007
	0.12	0.097	0.999	0.097	0.095	0.002
	0.14	0.020	0.999	0.020	0.020	0.000

1 STUDY DESIGN

QDOT MICRO IDE (IDE # G180176) is a prospective, non-randomized, pre-market clinical evaluation of the QDOT MICROTM Catheter to demonstrate the safety and effectiveness against performance goals. The trial includes 1.) Main study: subjects treated using the nMARQ RF generator with constant flow rate (8mL/min) for QMODE+ applications, and 2.) Variable Flow study: subjects treated with the nMARQ RF generator with variable flow rate (4-15 ml/min) for QMODE+ applications.

The goal of the Variable Flow study is to demonstrate safety and effectiveness for the variable flow configuration of the device. A total of 92 enrolled subjects is planned. Enrollment in the Variable Flow study will begin when enrollment in the main study is completed.

The analysis for the Main study is a stand-alone analysis and it is not dependent on data from the Variable Flow study. The results from the Variable Flow study will only be used for additional claims on the safety and effectiveness of the variable flow feature of the device.

2 TREATMENT ASSIGNMENT

All subjects in the Variable Flow study will be treated using the QDOT MICRO[™] catheter with variable flow rate.

3 RANDOMIZATION AND BLINDING PROCEDURES

All subjects will receive treatment with the QDOT MICRO catheter using variable flow rate. Therefore, no masking of treatment assignment for operators and subjects will be performed.

However, several measures will be employed to minimize operational bias:

- Screening logs will be maintained at sites to confirm consecutive eligible subjects are considered for participation in the study
- Sponsor personnel directly involved in the conduct of the study will not have access to intermediate aggregated summaries of primary safety and effectiveness endpoint data until preparation for filing for approval

4 LEVEL OF SIGNIFICANCE

Both primary safety and effectiveness endpoints will be tested at the one-sided 2.5% significance level. All confidence intervals will be presented at the 95% confidence level unless otherwise specified.

5 ANALYSIS SETS

The following analysis sets will be used for the Variable Flow study:

- Safety Analysis Set: The Safety analysis set will include all enrolled subjects in the Variable Flow study who have the investigational device inserted, regardless of RF energy delivery.
- Modified Intent-To-Treat (mITT) Analysis Set: The mITT analysis set will consist of all enrolled subjects in the Variable Flow study who meet all eligibility criteria and have the investigational device inserted. Subjects in this analysis set who are discontinued due to reasons related to the QDOT MICROTM catheter will be considered as acute effectiveness failures; subjects who are discontinued due to reasons not related to the QDOT MICROTM catheter will not be considered as acute effectiveness failures.
- **Per Protocol (PP) Analysis Set:** The PP analysis set will include subjects in the Variable Flow study who satisfy the following criteria:
 - Enrolled and meet eligibility criteria
 - Have undergone RF ablation
 - Are treated with the study catheter, and have been treated for the study related arrhythmia
 - without major protocol deviations:
 - Missing all protocol-specified electronic effectiveness monitoring
 - Esophageal monitoring is not done per protocol and risk is not mitigated
 - Not following the required waiting period of 20 minutes before pacing procedures, and/or infusion of cardiac medications to induce AF/reconnection is not performed before entrance block confirmation
 - Undergoing the ablation procedure with a constant flow rate in place of the variable flow rate

6 SAMPLE SIZE JUSTIFICATION

The final analyses for primary safety and effectiveness endpoints in the Variable Flow study will apply Bayesian methods using a beta-binomial model with data borrowing from the Main study using a propensity score-integrated power prior approach. Based on a PG of 14% for the primary safety endpoint and a PG of 50% for the primary effectiveness endpoint, and allowing borrowing up to 91 subjects from QDOT MICRO (IDE # G180176) Main study, the sample size of 92 subjects in the Variable Flow study provides close to 80% power at a one-sided significance level of 2.5% to declare success for both the safety and effectiveness endpoints, assuming the true PAE rate is 7% and the true effectiveness failure-free rate is 65%. It is also assumed that there is a 5% and 12%

attrition rate for the safety and effectiveness endpoints in the Variable Flow study, respectively. More details about the borrowing strategy are provided in section 7.4.

7 STATISTICAL ANALYSIS METHODS

7.1 General Conventions

Standard descriptive summaries for continuous variables will include the number of observations with data, mean, standard deviation, median, 25% percentile, 75% percentile, minimum and maximum values. For categorical variables, the count and percentage will be provided. Percentages will be based on the number of subjects without missing data.

7.2 Subject Disposition

Disposition and accountability of the study subjects will be summarized descriptively for the subject categories defined in section 9.5 of the protocol.

7.3 Demographic and Baseline Characteristics

Subject demographics, medical history, AAD use history and other baseline data will be summarized descriptively for all enrolled subjects as well as subjects in the Safety, mITT and PP analysis sets.

7.4 Borrowing Approach

A propensity score-integrated power prior approach will be used to borrow data from the Main study for evaluating safety and effectiveness of the Variable Flow study. The borrowing approach follows the method described in Yue, L. et al¹, and ensures that we only borrow data from subjects in the Main study who are similar to the subjects in the Variable Flow study in terms of their baseline characteristics. The catheter design and the procedure workflow with the exception of the flow rate are identical between the Main study and the Variable Flow study. Preclinical and bench testing concluded comparable performance of the catheter for constant or variable flow rates. Accordingly, data from up to 91 subjects in the Main study will be borrowed for the Variable Flow study.

The following two-stage strategy will be used for borrowing :

1st Stage (Build the propensity score model) :

Using mITT analysis set, the propensity score model will be developed using assignment to the two studies (Main study vs. Variable Flow study) as the outcome, and demographics and

¹ Wang C, Li H, Chen WC, Lu N, Tiwari R, Xu Y, Yue L. Propensity score-integrated power prior approach for incorporating realworld evidence in single-arm clinical studies. Journal of Biopharmaceutical Statistics. 2019, 29:5, 731-748. Version 2.0 VFlow – July 22, 2021 Biosense Webster, Inc Page 7 of 16

baseline characteristics as covariates in a logistic regression model. Covariates to be included are the following :

- a. Demographics : age (age \geq 75, age 65-74 years, and age < 65), gender, BMI
- b. Baseline : left ventricle ejection fraction, LA diameter
- c. Medical conditions prior to enrollment: hypertension, thromboembolic events including stroke/TIA, Type II diabetes, obstructive sleep apnea (OSA), pericardial effusion, mitral valve regurgitation, and type of arrythmia, congestive heart failure, vascular disease history
- d. History of symptomatic paroxysmal AF: total duration of PAF, total number of episodes in the past 12 months
- e. Previous treatment for arrhythmia: pharmacological cardioversion (PCV), direct current cardioversion (DCCV), catheter ablation procedure, number of previously failed AADs

An independent statistician who has no access to the main study outcomes will be identified after enrollment is complete but prior to completion of follow-up in the Variable Flow study to build the propensity score model. For the modeling, any missing data or outliers (e.g. a subject with loop recorder may have a excessively large value for the history of symptomatic paroxysmal AF) will be imputed by randomly drawing from the distribution of the corresponding covariate.

2nd Stage (Determine Borrowing) :

Once the propensity score model is built by the independent statistician, the Sponsor will proceed to determine borrowing. This will be done after completion of enrollment in the Variable Flow study but prior to completion of follow-up. Let *N* denote one subject less than the number of subjects in the mITT analysis set in the Variable Flow study :

- I. The subjects in the Main study will be trimmed if their propensity scores are outside of the range of propensity scores for the subjects in the Variable Flow study.
- II. Subjects will be grouped into 5 strata (quintiles) based on the propensity score ranking such that the same number of Variable Flow study subjects are in each propensity score stratum.
- III. The balance of covariate distributions will be assessed graphically between subjects in the Main study and the Variable Flow study.
- IV. The similarity measurement (r_s) will be calculated using the Kolmogorov-Smirnov (KS) distance for each propensity score stratum. Let KS_s denotes the maximum distance between the empirical distribution functions of the observed propensity score in the Main study and the Variable Flow study for the *s*-th stratum. Then the similarity measurement for the *s*-th stratum will be obtained by

$$r_s = 1 - KS_s.$$

V. The number of subjects to be borrowed from the Main study in each stratum will be based on similarity to the Variable Flow study. The standardized similarity measurement for each stratum is obtained by $r_s / \sum r_s$ and the number of Main study subjects to be borrowed from each stratum is obtained by $Nr_s / \sum r_s$.

Let $n_{s,Main}$ and $n_{s,Flow}$ be the number of subjects in the Main study and the Variable Flow study in the *s*-th stratum, respectively. For the Variable Flow study, subjects with missing outcomes will be excluded to obtain the following posterior distributions. The power term controlling the amount of information borrowed from the Main study for each stratum is obtained by $\alpha_s = \min\left(\frac{Nr_s/\Sigma r_s}{n_{s,Main}}, 1\right)$.

Let $y_{s,Flow}$ and $y_{s,Main}$ be the number of subjects with PAEs in the Variable Flow study and the Main study respectively in the *s*-th stratum. Assuming non-informative Beta(0.5, 0.5) prior for safety, the resulting posterior distribution for the safety endpoint for each stratum is Beta(0.5 + $Y_{s,borrow}$ + $y_{s,Flow}$, 0.5 + $NY_{s,borrow}$ + $(n_{s,Flow} - y_{s,Flow})$), where $Y_{s,borrow}$ = min ($\alpha_s \times y_{s,Main}, y_{s,Flow}$) and $NY_{s,borrow}$ = min ($\alpha_s \times (n_{s,Main} - y_{s,Main}), (n_{s,Flow} - y_{s,Flow})$).

Let $x_{s,Flow}$ and $x_{s,Main}$ be the number of subjects that are failure-free through 12 months in the Variable Flow study and the Main study respectively in the *s*-th stratum. Similarly, assuming non-informative Beta(1, 1) for the effectiveness endpoint, the resulting posterior distribution for the effectiveness endpoint for each stratum is Beta $(1 + X_{s,borrow} + x_{s,Flow}, 1 + NX_{s,borrow} + (n_{s,Flow} - x_{s,Flow}))$, where $X_{s,borrow} = \min (\alpha_s \times x_{s,Main}, x_{s,Flow})$ and $NX_{s,borrow} = \min (\alpha_s \times (n_{s,Main} - x_{s,Main}), (n_{s,Flow} - x_{s,Flow})))$. Only subjects with non-missing endpoint data in the main arm will be included for borrowing in the corresponding endpoint analyses. The posterior distributions of the primary endpoints are obtained by a weighted average of the posterior distributions across the 5 strata using equal weights.

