## Study Success

The study will be considered successful if the primary endpoints are met for main study. If the main study is not successful, the data for the second (variable flow) study will not

	Biosense Webster, Inc	
Version 5.0 – Feb 3, 2021	CONFIDENTIAL	Page 100 of 135

be submitted for labeling. The second (variable flow) study will be considered successful if both the primary safety and primary effectiveness performance goals are met.

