#### 18.5 Levels of Significance

The type I error for the interim and final analyses of the primary endpoints for the main study is controlled at one-sided 2.5%. Two-sided 95% confidence intervals will be presented around the percentages unless otherwise specified. For the variable flow study, both primary endpoints will be tested at the end of the study at the 2.5% significance level, and all confidence intervals will be presented at the 95% confidence level unless otherwise specified.

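### SAP 7.4 caps borrowed PAEs and non-PAEs separately, so with both studies at the 14% goal the Variable Flow safety test has about 7% false success, not the stated one-sided 2.5%

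*SAP*

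**What the plan says.** SAP 7.4 (second stage) discounts Main study data in each of five propensity strata by a power term `α_s`. It then applies two further limits for safety. Borrowed PAEs are "Y_{s,borrow}$ = min ($\alpha_s \times y_{s,Main}, y_{s,Flow", that is, at most the VF PAE count. Borrowed non-PAEs are limited in the same way by the VF non-PAE count. Effectiveness uses the same construction, starting with "X_{s,borrow} = \min (\alpha_s \times x_{s,Main}, x_{s,Flow". The stratum posteriors are "obtained by a weighted average of the posterior distributions across the 5 strata using equal weights".

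The level is stated in several places:
- SAP 4: "Both primary safety and effectiveness endpoints will be tested at the one-sided 2.5% significance level".
- Protocol 18.5, for the VF study: "both primary endpoints will be tested at the end of the study at the 2.5% significance level".
- SAP 6: the design "provides close to 80% power at a one-sided significance level of 2.5% to declare success for both the safety and effectiveness endpoints". Protocol 18.7 and the protocol summary also give 2.5% for VF.

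Two statements limit how VF results are used. Protocol section Study Success: "If the main study is not successful, the data for the second (variable flow) study will not" be submitted for labelling. SAP 1 confines VF results to "additional claims on the safety and effectiveness of the variable flow feature of the device".

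Protocol Appendix D reports simulated type I error for the Main study only. The contents list names a VF type I error section in an Appendix E whose text is not in the protocol, so no VF figure can be seen.

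**The concern.** The power term already controls how much is borrowed. The two extra minima change what is borrowed. PAEs are rare, so a stratum of about 17–18 evaluable VF subjects expects only about 2.4 PAEs at 14%. The PAE cap therefore cuts deep relative to the count it acts on, and the non-PAE cap does not. It also cuts most when VF happens to show few PAEs, which is when the test is likely to pass.

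The borrowed data then look safer than Main was, and the stated 2.5% is not the level of the rule in the SAP. At stake is a primary safety conclusion about the variable flow feature.

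**Working it through.** **Inputs.** VF 92 enrolled (SAP 1); Main 185 (protocol 8.1); five strata and `N` = 92 − 1 = 91 (SAP 7.4); attrition 5% for safety and 12% for effectiveness (SAP 6); safety prior Beta(0.5, 0.5), effectiveness prior Beta(1, 1); goals 14% and 50%; threshold 0.975 (SAP 7.5, 7.6).

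**Assumptions not in the documents.** Main attrition equals the VF figures. The base case has no covariate imbalance. The weighted average is the mean of the five stratum rates. Ranges below cover two readings of `n_s,Main`: all trimmed Main subjects, or only those with an outcome.

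**Main study first.** With 185 subjects and a Beta(1, 1) prior, Main safety passes with 16 or fewer PAEs. At a true 14% this has probability 0.019; Appendix D shows 0.020–0.023. The Main figure is therefore reproduced closely. The VF 2.5% is not.

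**One stratum by hand.** With equal similarity, `α_s` = (91/5)/(185/5) = 18.2/37 = 0.492. Take VF 1 PAE in 18 and Main 5 in 37 (13.5%).
- Discounted Main PAEs: 0.492 × 5 = 2.46. Non-PAEs: 0.492 × 32 = 15.74.
- Borrowed PAEs: min(2.46, 1) = 1. Borrowed non-PAEs: min(15.74, 17) = 15.74.
- Borrowed rate: 1/16.74 = 6.0%, against 13.5% in Main.

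**Average over trials, both studies at 14%.** With equal strata, the rule borrows 8.6 PAEs and 70.8 non-PAEs, a rate of 8.6/79.4 = 10.8%. Without the caps it borrows 12.1 and 74.0, a rate of 14.0%. The caps remove 1 − 8.6/12.1 = 29% of PAEs and 1 − 70.8/74.0 = 4% of non-PAEs. With propensity scores simulated, trimmed and stratified as in SAP 7.4, they remove 29–31% and 6–8%, and the borrowed rate is 10.9–11.0%.

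**False success, safety** (20,000 trials per scenario; standard error about 0.2 points at 7%):

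| True PAE rate, Main / VF | SAP 7.4 rule | Without caps |
|---|---|---|
| 14% / 14% | about 7% | 0.3–0.4% |
| 12% / 14% | about 8–9% | 1.3–1.6% |
| 10% / 14% | about 10–11% | about 4% |
| 7% / 14% | about 17–18% | 14–16% |

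With no borrowing, the error at a VF rate of 14% is 0.6–0.8%. Other stratum sizes and attrition patterns with `N` = 91 give 7.0–8.3% at 14%/14%; `N` = 80 gives 5.4%. A 0.5 SD propensity shift gives 6.6–7.1%.

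**False success, effectiveness:**

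| True failure-free rate, Main / VF | SAP 7.4 rule | Without caps |
|---|---|---|
| 50% / 50% | about 4.6–5.7% | 1.1–1.4% |
| 65% / 50% | 16–18% | 46–54% |

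The mechanism differs here. At 50% the borrowed rate is unbiased, but capped counts partly copy the VF counts. The correlation between the VF rate and the borrowed rate is 0.75–0.87, against 0.00 without caps, so VF data are partly counted twice.

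**Power at 7% and 65%.** Safety is 86–88% as written and about 77–78% without caps. Effectiveness as written is 95–96%. Joint power, as the product, is 82–83% as written. With safety uncapped and effectiveness as written it is about 74–76% (for example 0.773 × 0.957 = 0.74).

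**The case against.** **The Main gate.** VF data go nowhere if Main fails. With Main at 14%, Main safety passes with probability about 0.021 (Appendix D). Given that pass, VF false success is about 0.136, so both occur in 0.021 × 0.136 = 0.3% of trials. That stands, and a reader who infers that 7% of unsafe devices would reach labelling goes too far. But the gate does not restore the level of the VF test itself, which is what SAP 4 and protocol 18.5 state.

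**Cap or borrowing.** A reader might blame the caps for the 17–18% at Main 7%/VF 14%. The table does not support that. Removing the caps still leaves 14–16%, so most of that error is the price of borrowing from a better Main study.

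**Effectiveness.** A reader might infer that the caps should go there too. They should not: at Main 65%/VF 50% the caps hold the error to 16–18% instead of 46–54%.

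**Reading of the average.** A literal mixture of the five posteriors gives false success near 0, but safety power of about 3%. That cannot be reconciled with the stated power.

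**Power as evidence of the intended rule.** The protocol summary gives close to 80% for safety alone, which fits the uncapped rule better (77–78% against 86–88%). Protocol 18.7 says overall power stays close to 80% with at least 80 subjects borrowed. At `N` = 80, safety power is about 85% capped and 74% uncapped, which favours the capped rule. The power statements do not settle which rule was simulated.

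**Conclusion.** The point holds for safety near equal rates. With both studies at 14%, the rule in SAP 7.4 has about 7% false success, nearly three times the stated one-sided 2.5%. There the separate caps cause the excess, because the same design without them runs at 0.3–0.4%. For effectiveness at 50%/50% the stated level is also exceeded, at about 4.6–5.7%, but the caps protect when Main is better, so the fault is in the stated level rather than the rule.

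The 7% rests on the mean-of-strata reading, 5% attrition in both studies and stratum sizes that the documents do not give; it was stable across the variants tried with `N` = 91. The documents do not support saying that no VF simulation was done, only that none is shown. Since VF carries a primary safety claim, the rule or the stated level has to change before analysis.

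**What to change.** 1. **Safety, SAP 7.4.** Delete the two minima and use the ordinary power-prior posterior in each stratum: `Beta(0.5 + α_s × y_s,Main + y_s,Flow, 0.5 + α_s × (n_s,Main − y_s,Main) + n_s,Flow − y_s,Flow)`. An alternative is one common factor per stratum that shrinks borrowed PAEs and non-PAEs together and keeps the Main ratio: `c_s = min(1, y_s,Flow/(α_s × y_s,Main), (n_s,Flow − y_s,Flow)/(α_s × (n_s,Main − y_s,Main)))`, omitting a term whose Main count is zero. Its error at 14%/14% is 1.6–2.0% and its power 79–80%. However, it makes borrowing depend on VF outcomes, and its error is higher than with plain deletion at Main 14%, 12% and 10%. Neither guarantees 2.5% when Main is better than goal, and the text should say so.
2. **Effectiveness.** Keep the caps. Replace the 2.5% statement in SAP 4, SAP 6 and protocol 18.5 (and where protocol 18.7 and the summary repeat it) with the simulated VF type I error of the rule.
3. **Reporting.** Restate joint power under the final rules (about 74–76% with item 1 by deletion and item 2). Tabulate VF type I error for both endpoints over equal and discordant Main/VF rates. Define the weighted average and `n_s,Main` explicitly.

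**Cost.** Roughly 8 to 11 points of safety power (86 − 78 to 88 − 77), text edits and a re-run of the simulations. No new data are needed.

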7.5 Analysis of Primary Safety Endpoint

The primary adverse event (PAE) rate will be compared against a performance goal of 14% by testing the following hypotheses:

$$H_0: p_s \ge 0.14$$
 vs $H_A: p_s < 0.14$,

where p_s is the PAE rate (please refer to the study protocol for the definition of the primary safety endpoint). The mITT Analysis Set is the primary analysis set for the primary safety endpoint.

The primary analysis for the primary safety endpoint will be based on data from the Variable Flow study with borrowing from the mITT analysis set in the Main study, and will apply Bayesian methods and use a beta-binomial model.

The primary safety endpoint will be met if

$$\Pr(p_S < 0.14 | y, n) > 0.975$$

where p_s is the PAE rate. If the posterior probability of the safety rate being less than 14% is greater than 0.975 then the study will be considered to have demonstrated safety for the variable flow rate.

The following additional sensitivity analyses will be performed by updating the resulting posterior distribution for the safety endpoint for each stratum in the 2nd stage in Section 7.4 after accounting for missing data. Since the power term α_s controlling the borrowing does not depend on the missing outcome, the posterior distribution for the safety endpoint for each stratum is updated by incorporating the missing safety outcomes according to each scenario. Borrowing from the main study remains unchanged from the primary analysis, i.e., sensitivity analyses will be performed for missing primary endpoint data in the Variable Flow study.

• Tipping Point Analysis

Tipping point analysis will be performed for the primary safety endpoint in the mITT analysis set to assess the impact of missing outcomes in the Variable Flow study on the primary safety analysis. The posterior distribution will be updated each time to evaluate whether a tipping point is identified.

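### SAP 7.4 combines the five stratum posteriors in words that describe a mixture, which is not the posterior of the overall rate tested; at the planning rates only averaging the stratum rates fits the stated power

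*SAP*

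**What the plan says.** SAP section 7.4 (2nd Stage) sets out the primary analysis of the Variable Flow study in detail. It forms five propensity strata with equal numbers of Variable Flow subjects, and gives formulas for the similarity measure, the power term, the caps on borrowed events and non-events, and a Beta posterior in each stratum. The stratum priors are Beta(0.5, 0.5) for safety and Beta(1, 1) for effectiveness. The last step has no formula, only this sentence: "The posterior distributions of the primary endpoints are obtained by a weighted average of the posterior distributions across the 5 strata using equal weights".

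Sections 7.5 and 7.6 then work with one study-level rate per endpoint. After the words "The primary safety endpoint will be met if", section 7.5 requires Pr(p_S < 0.14) to exceed 0.975. Section 7.6 requires Pr(p_E > 0.5) to exceed 0.975.

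On power, SAP section 6 says that "the sample size of 92 subjects in the Variable Flow study provides close to 80% power at a one-sided significance level of 2.5" percent for declaring success on both endpoints, "assuming the true PAE rate is 7% and the true effectiveness failure-free rate is 65" percent. Protocol section 18.7 says the same, and adds that power holds up when at least 80 Main study subjects are borrowed. Protocol section 18.9.4 leaves the details of borrowing to the SAP, so no other place in the documents settles the combination step.

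**The concern.** A weighted average of distributions is a mixture. Drawing from it means picking one stratum at random and drawing that stratum's rate. Its spread is the spread of a single stratum (about 18 Variable Flow subjects plus what is borrowed for that stratum), with the differences between strata added on top.

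The quantity tested in sections 7.5 and 7.6 is the overall rate, which under equal weights is the mean of the five stratum rates. Its posterior comes from averaging five independent draws and is much narrower.

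Both distributions have the same mean, but the decision rule uses a tail probability. A programmer who follows the sentence word for word applies the 0.975 threshold to a distribution far wider than that of the rate being tested. If the ambiguity is settled only after outcomes are known, the choice of reading could decide the study and would look post hoc.

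**Working it through.** **Inputs from the documents.**
- Performance goals of 14% and 50%, planning rates of 7% and 65%, 92 Variable Flow subjects, borrowing up to 91, and attrition of 5% (safety) and 12% (effectiveness): SAP section 6.
- Five strata, priors, power term and caps: SAP section 7.4.
- Threshold of 0.975 for each endpoint: SAP sections 7.5 and 7.6.
- 185 Main study subjects: Protocol Appendix D.

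**Assumptions.** The documents give neither the similarity values r_s nor the Main study stratum sizes. Main study subjects are spread at random and evenly over the strata, and r_s is equal across strata. A variant with r_s between 0.6 and 0.95 was also run. True rates and attrition are the same in both studies.

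**Step 1: spread under each reading.** Let v be the variance of one stratum posterior, taken as equal across strata.
- Mixture: variance = v + variance between the stratum means, so at least v.
- Mean of the rates: variance = (5 × v)/25 = v/5.
- The standard deviation therefore differs by a factor of at least √5 ≈ 2.2.

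**Step 2: one worked case.** Put every stratum exactly at its planning rate and use the average borrowing that the capped rule produced in simulation (80.9 subjects for safety, 70.5 for effectiveness).
- Safety, per stratum: 92 × 0.95/5 + 80.9/5 = 17.5 + 16.2 = 33.7 subjects. The posterior is Beta(0.5 + 33.7 × 0.07, 0.5 + 33.7 × 0.93) ≈ Beta(2.86, 31.8), with mean 0.082 and SD 0.046. The goal of 0.14 lies (0.14 − 0.082)/0.046 ≈ 1.3 SDs away. Under the mixture, Pr(p < 0.14) ≈ 0.89. For the mean of the rates the SD is 0.046/√5 ≈ 0.021 and the probability is about 0.99.
- Effectiveness, per stratum: 92 × 0.88/5 + 70.5/5 = 16.2 + 14.1 = 30.3 subjects. The posterior is Beta(1 + 30.3 × 0.65, 1 + 30.3 × 0.35) ≈ Beta(20.7, 11.6), with mean 0.641 and SD 0.083. The goal of 0.50 lies about 1.7 SDs away. Under the mixture, Pr(p > 0.50) ≈ 0.95. For the mean of the rates it is above 0.999.

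With data exactly as planned, the mixture misses 0.975 on both endpoints and the mean of the rates passes on both.

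**Step 3: reproducing the stated power.** The whole rule was simulated at 7%/65%, with 4,000 to 20,000 trials per setting:

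| Reading | Caps | Safety | Effectiveness | Both |
|---|---|---|---|---|
| Mean of stratum rates | yes | about 87% | about 95-96% | 82-84% |
| Mean of stratum rates | no | about 78% | about 98-99% | 76-79% |
| Mixture, as worded | yes | about 3% | about 7-8% | 0.2-0.3% |
| Mixture, as worded | no | about 0.5% | about 6-8% | under 0.1% |

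The SAP's joint figure of close to 80% lies between the two rows for the mean of the rates. A single pooled Beta gives 87-90% jointly and fits less well. Varying r_s moves the joint figure for the mean of the rates by only one or two points.

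**Step 4: dependence on the true rates.** Joint success under the mixture, with caps:

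| True rates (adverse event / failure-free) | Joint success, mixture |
|---|---|
| 5% / 70% | 5% |
| 3% / 75% | about 39% |
| 2% / 80% | 77% |
| 1% / 85% | 97% |

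The mean of the rates gives about 99% or more in each of these settings.

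**The case against.** The strongest reply is that the intention can be recovered. Sections 7.5 and 7.6 define p_S and p_E as single study-level rates, a mixture of stratum densities is not the posterior of such a rate, and the stated power comes out only when the rates are averaged. This stands, and it is why the sentence is best seen as wrong wording on a decisive step. It does not remove the point: the sentence names the distributions as the thing averaged, and a pre-specified primary analysis should not have to be inferred from its power statement.

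A second reply is that SAP section 7.4 refers to a cited methods paper, which may define the step. That cannot be checked from the documents, and a reference does not override an explicit sentence in the SAP.

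A third reply is that little is at risk. The mixture is the stricter reading, so the harm is a missed success and not a false claim. The Main study analysis stands alone, and the Variable Flow results serve only additional claims. This also stands, and it limits the consequence to the Variable Flow study.

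A reader might infer that the Variable Flow study was sized to fail, or has almost no chance of success. The documents do not support either. The power calculation evidently used the averaged rates, and the near-zero figure belongs to the literal mixture close to the planning rates. At 3%/75% even the mixture succeeds jointly in about 39% of trials.

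**Conclusion.** The point holds. Followed literally, the last sentence of SAP section 7.4 produces a mixture, which is the wrong distribution for the rates tested in sections 7.5 and 7.6 and contradicts the plan's own power. At 7%/65% with the SAP caps, joint success is about 0.3% under the mixture and about 83% under averaged rates (76-79% without caps), against a stated figure of close to 80%. Averaging was probably intended.

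The percentages rest on assumed similarity values, assumed Main study stratum sizes and equal true rates in the two studies. The gap is far too large for those assumptions to explain. It narrows as the true rates improve, and its direction is towards missed success.

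This check concerns how the strata are combined. It does not establish that the averaged rule controls type I error under the caps: with both studies at both goals, it met safety in about 7% and effectiveness in about 5% of simulated trials, which deserves a separate check.

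**What to change.** Before outcomes are analysed, replace the last sentence of SAP section 7.4 with:

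*The overall rate is p = (p_1 + p_2 + p_3 + p_4 + p_5)/5. Its posterior is obtained by drawing p_s independently from each stratum Beta posterior and averaging the five draws. Pr(p < 0.14) for safety and Pr(p > 0.50) for effectiveness are evaluated from these averaged draws.*

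The sponsor should also confirm that the simulations behind section 6 used this construction, and with the caps. The cost is one sentence and that confirmation. Sample size, borrowing limit, thresholds and data collection do not change.
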